To evaluate the efficacy in disease control of enpatoran compared to placebo in lupus participants with active lupus rash	 Endpoints: Change from Baseline in CLA-IGA at Week 16 and Week 24 Change from Baseline in Physician's Global Assessment of Cutaneous Lupus Disease Activity at Week 16 and 24 Population: Patients with active SCLE, DLE, or SLE with active lupus rash Note: Active SCLE, DLE and SLE participants from Cohort A OR Cohort B with CLASI-A≥8 at Screening and confirmed at Day 1 CCI Population-Level Summary: LS mean (SE) at each visit and treatment difference (95% CI) as estimated by MMRM. 	
To demonstrate the effect of enpatoran compared with placebo on achieving both BICLA response and clinically meaningful CS reduction in SLE participants on prednisone ≥ 10 mg at Day 1		
To evaluate the efficacy in disease control of enpatoran compared to placebo in lupus participants with predominantly active lupus rash	Endpoints: Clinically meaningful CS reduction, defined as reduction of daily prednisone-equivalent dose from ≥ 10 mg at Day 1 to ≤ 5 mg by the Week 12 visit and sustained through Week 24 Cocurrence of CLA-IGA 0 or 1 at Week 16 and Week 24	

Objectives	Estimand attributes
	Population: Patients with active SCLE, DLE, or SLE with predominantly active lupus rash Note: Active SCLE, DLE and SLE participants from Cohort A COL Population-Level Summary: number and proportion with 95% CI of participants achieving the respective response definition at Week 12 and Week 24.
To evaluate the efficacy in disease control of enpatoran compared to placebo in participants with active SLE	Endpoints: SRI-4 response at Week 24 Remission attainment at Week 24 Clinically meaningful CS reduction, defined as reduction of daily prednisone-equivalent dose from ≥ 10 mg at Day 1 to ≤ 5 mg by the Week 12 visit and sustained through Week 24 Population: Patients with active SLE Note: Cohort B participants CI Population-Level Summary: Number and proportion with 95% CI of participants achieving the respective response definition at Week 24. Endpoint: Change from Baseline in Physician's Global Assessment at Week 24 Population: as above CI Population: as above CI Population-Level Summary: Summary statistics at each visit

Objectives	Estimand attributes
	Endpoint: Change in the number of joints which are tender and swollen in 28-joint count from Baseline at Week 24
	Population: Patients with active SLE and at least 4 active joints

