9.4.1 Efficacy Analyses

9.4.1 Efficacy Analyses		
Endpoints	Statistical Analysis Methods	
Primary		
Percent change from Baseline in CLASI-A at Week 16	This endpoint will be analyzed for CLE (active SCLE and/or DLE) and SLE participants from Cohort A as described in Section 9.4.1.1	
BICLA response at Week 24	This endpoint will be analyzed for Cohort B SLE participants as described in Section 9.4.1.2	
Secondary		
	vill be analyzed for CLE (active SCLE and/or DLE) and SLE participants ASI-A ≥ 8 at Screening and confirmed at Day 1	
Change from Baseline in CLA-IGA at Week 16 and Week 24 Change from Baseline in Physician's Global Assessment of Cutaneous Lupus Disease at Week 16 and Week 24	MMRM analysis will be used to model the score at each visit through Week 24 with terms for intervention group, visit, intervention group by visit interaction, Baseline score, and randomization stratification factors. Test and treatment effect estimator (with 95% 2-sided CI) based on difference (enpatoran versus placebo) in least squares means of Week 24% CFB (or CFB respectively) from the model. Cumulative distribution function for Week 24 CFB will be estimated by intervention group. Missing data assumed to be missing at random (MAR), with missing data status noninformative. Descriptive statistics will be provided at each visit.	
Occurrence of CLA-IGA 0 or 1 at Week 16 and Week 24	This endpoint will be analyzed using the logistic regression model, with the covariates based on the randomization stratification factors. Test and treatment effect estimator (with 95% 2-sided CI) will be based on the odds ratios (each enpatoran versus placebo) in participants with prednisone-equivalent dose \geq 10 mg at Day 1. Descriptive statistics will be provided.	

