Change from Baseline in the Skindex 29+3 symptom domain score at Week 24 Change from Baseline in the Skindex 29+3 Functioning and Emotion domain scores at Week 24 Change from Baseline in the Skindex 29+3 lupus-specific domain score at Week 24	MMRM analysis where score CFB at each visit through Week 24 is modeled, with terms for intervention group, visit, intervention group by visit interaction, Baseline score, and randomization stratification factors. Test and treatment effect estimator (with 95% 2-sided CI) based on difference (enpatoran versus placebo) in least squares means of Week 24 CFB from the model. Cumulative distribution function for Week 24 CFB will be estimated by intervention group. Missing data assumed to be missing at random (MAR), with missing data status noninformative for CFB. Descriptive statistics will be provided at each visit.	
The following secondary endpoints v Cohort A and Cohort B	vill be analyzed for CLE (active SCLE and/or DLE) and SLE participants from	
Clinically meaningful CS reduction, defined as reduction of daily prednisone-equivalent dose from ≥ 10 mg at Day 1 to ≤ 5 mg by the Week 12 visit and sustained through Week 24	This endpoint will be analyzed using the logistic regression model, with the covariates of the randomization stratification factors. Test and treatment effect estimator (with 95% 2-sided CI) will be based on the odds ratios (each enpatoran versus placebo) in participants with prednisone-equivalent dose ≥ 10 mg at Day 1. Descriptive statistics will be provided	

Enpatoran (M5049) The WILLOW study with enpatoran in SLE and CLE (SCLE and/or DLE) MS200569_0003

[figure not shown]
Endpoints	Statistical Analysis Methods
Change from Baseline in FACIT-Fatigue scores at Week 24	MMRM analysis where score CFB at each visit through Week 24 is modeled, with terms for intervention group, visit, intervention group by visit interaction, Baseline score, and randomization stratification factors. Test and treatment effect estimator (with 95% 2-sided CI) based on difference (enpatoran versus placebo) in least squares means of Week 24 CFB from the model. Cumulative distribution function for Week 24 CFB will be estimated by intervention group. Missing data assumed to be MAR, with missing data status noninformative for CFB.
	Descriptive statistics will be provided at each visit.
The following secondary endpoints w	vill be analyzed for SLE participants from Cohort B

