Attributes of the estimands are described in the table below:

Endpoint	Clinically meaningful CS reduction, defined as reduction of daily prednisone-equivalent dose from ≥ 10 mg at Day 1 to ≤ 5 mg by the Week 12 visit and sustained through Week 24
Population(s)	 SLE participants (Cohort B) with daily prednisone-equivalent dose ≥ 10 mg at Day 1 Cohort A participants with daily prednisone-equivalent dose ≥ 10 mg at Day 1
Treatment	Enpatoran vs placebo
Population-level summary measure	Odds ratio (conditional on stratification factors) between each active dose and placebo

Clinically meaningful CS reduction at Week 12 will be assessed based on the "CORTICOSTEROID MEDICATION DETAILS" form. Sustainment of the reduction will be assessed throughout the period between Week 12 and Week 24 (see appendix 18.2 for derivation of daily prednisone-equivalent dose).

A composite estimand strategy will be applied to handle the intercurrent events. Participants who experience any of these intercurrent events will be considered as not achieving CS reduction.

Descriptive Analysis

The number and percentage of participants with a clinically meaningful CS reduction will be provided.

Inferential Analysis

A logistic regression of clinically meaningful CS reduction status (yes/no) on the study intervention groups as a categorical variable and the stratification factors (see Section 14) will be fitted.

Odds ratios together with their 95% CI will be provided for each enpatoran group vs placebo. Treatment effect (and 95% CI) on the probability scale will also be provided.

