14.3.4 BICLA Response and Clinically Meaningful CS Reduction

This estimand will be analyzed at the final analysis. Its attributes are described in the table below:

Endpoint	BICLA response and clinically meaningful CS reduction, defined as reduction of daily prednisone-equivalent dose from ≥ 10 mg at Day 1 to ≤ 5 mg by the Week 12 visit and sustained through Week 24
Population(s)	SLE participants (Cohort B) with daily prednisone-equivalent dose ≥ 10 mg at Day 1
Treatment	Enpatoran vs placebo

Population-level	Odds ratio (conditional on stratification factors) between each active dose and placebo
summary measure	

A composite estimand strategy will be applied to handle the intercurrent events. Participants who experience any of these intercurrent events will be considered as non-responder.

Participants will be considered as responders if they have a BICLA response at Week 24 and a clinically meaningful CS reduction from ≥ 10 mg at Day 1 to ≤ 5 mg by the Week 12 visit sustained through Week 24 was observed (see section 14.3.3). If BICLA response is missing at Week 24, it will be considered as a non-response (see Section 14.2.1).

Descriptive Analysis

The number and percentage of participants with a BICLA response and a clinically meaningful CS reduction will be provided.

Inferential Analysis

A logistic regression of the BICLA response and clinically meaningful CS reduction status (yes/no) on the study intervention groups as a categorical variable and the stratification factors will be fitted.

Odds ratios together with their 95% CI will be provided for each enpatoran group vs placebo. Treatment effect (and 95% CI) on the probability scale will also be provided.

14.3.5 CLA-IGA 0 or 1 at Week 16 and Week 24

Estimands attributes are described in the table below.

Endpoint(s)	 Occurrence of CLA-IGA 0 or 1 at Week 16 Occurrence of CLA-IGA 0 or 1 at Week 24
Population(s)	 Cohort A Cohort B with CLASI-A ≥ 8 at Screening and confirmed at Day 1
Treatment	Enpatoran vs placebo
Population-level summary measure	Odds ratio (conditional on stratification factors) between each active dose and placebo

Descriptive Analysis

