The number and percentage of participants who have a CLA-IGA score of 0 or 1 ("clear" or "almost clear") will be provided at each scheduled visit. Participants experiencing an intercurrent event prior to the visit of interest will be considered as not having a CLA-IGA score of 0 or 1. A line plot depicting the percentage of responders over time grouped by study intervention group will also be provided.

Inferential Analysis

The same analysis as described in section 14.3.3 will be performed to assess the treatment effect on the occurrence of CLA-IGA 0 or 1 at Week 16 and Week 24.

Some CLA-IGA assessments have been conducted while Investigators were not trained. To assess the impact of the training on the results observed, descriptive and inferential analyses described in this section will be replicated using assessments collected on or after Investigator's training only.

14.3.6 SRI-4 Response through Week 24

This analysis will be conducted at the final analysis. Attributes of the estimand are described in the table below.

Endpoint	Systemic lupus erythematosus Responder Index-4 (SRI-4) response at Week 24
Population(s)	SLE participants (Cohort B)
Treatment	Enpatoran vs placebo
CCI	
Population-level summary measure	Odds ratio (conditional on stratification factors) between each active dose and placebo

The systemic lupus erythematosus responder index-4 (SRI-4) response is a measure of reduced SLE disease activity. A participant is an SRI-4 responder at a given time-point if they achieve:

- CC
- No worsening of ≥ 0.3 points in PGA of SLE disease activity score compared to Baseline (PGA score expressed on a 0-3 scale) AND
- No new BILAG A organ domain scores and ≤ 1 new BILAG B organ domain score compared to Baseline using BILAG 2004

Imputation of missing items will be performed for CCI, PGA of SLE disease activity and BILAG questionnaires as described in section 9.11. If SRI-4 response is still missing after imputation at a visit, the participant will be considered as a non-responder.

Descriptive Analysis

SRI-4 response will be summarized using descriptive statistics (frequency and percentage) at each ontreatment scheduled visit. The number and percentage of participants meeting each SRI-4 component

[figure not shown]
criterion will be provided during the on-treatment period. Additionally, a line plot depicting the percentage of responders over time grouped by study intervention group will also be provided.

Inferential analysis

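### Protocol 9.4.1 limits the CLA-IGA 0/1 odds ratio to participants on at least 10 mg prednisone-equivalent, contradicting the endpoint's own population, and the SAP drops the limit without declaring it

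*Protocol*

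**What the plan says.** **Protocol, objectives (Sections 1.1 and 3).** CLA-IGA 0 or 1 at Weeks 16 and 24 is a secondary endpoint. Its population is "Patients with active SCLE, DLE, or SLE with predominantly active lupus rash Note: Active SCLE, DLE and SLE participants from Cohort A". No steroid dose is mentioned.

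**Protocol 9.4.1, CLA-IGA 0/1 row.** The row sits under a heading, partly lost in the public text, that covers CLE and SLE participants with CLASI-A of at least 8 at Screening and Day 1. The method is logistic regression on the stratification factors, and the test and estimate "will be based on the odds ratios (each enpatoran versus placebo) in participants with prednisone-equivalent dose" of at least 10 mg at Day 1.

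**Protocol 9.4.1, steroid-reduction row.** Further down the same table, the odds ratio is again for "each enpatoran versus placebo) in participants with prednisone-equivalent dose ≥ 10 mg at Day 1". Here the endpoint is a fall from at least 10 mg to at most 5 mg, so the condition belongs.

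**SAP 14.3.5.** The endpoint, "Occurrence of CLA-IGA 0 or 1 at Week 16" and likewise at Week 24, has two populations: Cohort A, and "Cohort B with CLASI-A ≥ 8 at Screening and confirmed at Day 1". Neither carries a dose condition. The inferential text then says: "The same analysis as described in section 14.3.3 will be performed to assess the treatment effect on the occurrence of CLA-IGA 0 or 1".

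**SAP 14.3.3.** This is the steroid-reduction section. Both of its populations are restricted, one of them being "Cohort A participants with daily prednisone-equivalent dose ≥ 10 mg at Day 1".

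**SAP Section 7.** The only listed change to the protocol's analyses concerns the definition of the full analysis set.

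**The concern.** The protocol gives one endpoint two incompatible analysis populations. The objectives tables and the row heading describe everyone with active rash; the method text beside the endpoint describes only those on at least 10 mg prednisone-equivalent at Day 1. No reason is offered for the limit, and the neighbouring skin endpoints (change in CLA-IGA, cutaneous physician's global assessment, Skindex) do not have it.

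The SAP moves back to the wider population but does not say so, and its pointer to 14.3.3 leads to a section defined on the restricted subset. Two programmers working from these texts could produce different odds ratios for the same table, each citing a governing document. The choice between them should be written down before the final analysis, not settled once results are visible.

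**Working it through.** **1. Populations side by side**

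| Source | Population for CLA-IGA 0/1 | Steroid condition |
|---|---|---|
| Protocol 1.1 and 3, objectives | Cohort A | none |
| Protocol 9.4.1, heading over the row | CLE and SLE with CLASI-A ≥ 8 | none |
| Protocol 9.4.1, text in the row | participants at or above the dose limit | ≥ 10 mg at Day 1 |
| SAP Section 5, objectives | Cohort A | none |
| SAP 14.3.5, estimand table | Cohort A; Cohort B with CLASI-A ≥ 8 | none |
| SAP 14.3.3, the section cited for method | Cohorts A and B at or above the dose limit | ≥ 10 mg at Day 1 |

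Among the places that define this endpoint, only the row text in Protocol 9.4.1 carries the condition. Its wording matches that of the steroid-reduction row. Carry-over is the likeliest explanation, though the documents do not say so.

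**2. Inputs for size**

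Cohort A has about 100 participants in four equal arms of 25 (Protocol 1.1 and 9.2). The share s on at least 10 mg at Day 1 appears nowhere. Inclusion criterion 13 accepts an immunomodulator/immunosuppressant or a topical steroid in place of an oral one, which allows a low share; doses up to 30 mg are permitted, which allows a high one. So s is an assumption and is shown as a range. The plan states no sample size, power or response rate for CLA-IGA 0/1, so there is no figure to reproduce.

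**3. Formulas**

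- Participants kept = 100 × s; per arm = 25 × s, assuming the same share in each arm.
- Standard-error inflation = 1/√s, assuming the same response rates inside and outside the subset.
- Pairwise power, two-sided 0.05, with assumed response rates p₁ = 15% and p₂ = 45% and p̄ = 30%: Φ{[0.30 − 1.96 × √(2 × 0.30 × 0.70/n)] / √[(0.15 × 0.85 + 0.45 × 0.55)/n]}, where n is the number per arm.

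**4. Results**

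| Assumed s | Kept | Per arm | Dropped | SE factor | Pairwise power |
|---|---|---|---|---|---|
| 100% (no restriction) | 100 | 25 | 0 | 1.0 | 65% |
| 70% | 70 | 17.5 | 30 | 1.2 | 49% |
| 50% | 50 | 12.5 | 50 | 1.4 | 37% |
| 30% | 30 | 7.5 | 70 | 1.8 | 23% |
| 20% | 20 | 5 | 80 | 2.2 | 16% |
| 10% | 10 | 2.5 | 90 | 3.2 | 10% |

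The normal approximation is poor in the lowest rows; they show direction only.

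**5. Can the model be fitted?**

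With four arms, three regions and two diagnoses, the Cohort A logistic model has 1 + 3 + 2 + 1 = 7 parameters. That is fragile on 10 to 20 participants. For comparison, SAP 8.2 runs a Cohort A subgroup analysis only if every level has at least 5 participants in each arm; at s = 20% the average is exactly 5.

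**The case against.** The SAP is the later and more detailed plan, and Protocol 9.4 lets it specify alternative methods. Its estimand table in 14.3.5 is unrestricted and agrees with the CLASI-A heading in Protocol 9.4.1. That stands and lowers the practical risk considerably.

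A reader might infer that the pointer to 14.3.3 imports the dose-restricted population. The documents do not support this as the natural reading. The sentence "The same analysis as described in section 14.3.3 will be performed to assess the treatment effect" falls under the inferential heading, while population is a separate row of each estimand table. The SAP uses the same shorthand elsewhere across different populations: 14.3.14 (FACIT-Fatigue, all of Cohort B) borrows from 14.3.13 (Skindex, Cohort B with rash). What remains is that 14.3.5 never says only the model is reused, and here the section it borrows from has exactly the restriction that the protocol states.

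A reader might also take SAP 14.3.5 for a newly invented population. It is not: it fits the 9.4.1 heading. The difference that remains is with the objectives tables, which name Cohort A only.

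Finally, the objectives tables summarise this endpoint by numbers and proportions in Cohort A without a dose limit, so the protocol clause restricts only the test and odds ratio. That is also correct. None of this removes the need to record the change: Protocol 9.4 says that analysis changes not requiring an amendment will be described in the SAP and the study report, and SAP Section 7 does not list this one.

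**Conclusion.** The clause in the CLA-IGA 0/1 row of Protocol 9.4.1 is wrong as written. It contradicts the row's heading, the objectives tables and SAP 14.3.5, and the SAP's departure from it is undeclared.

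The size of the effect depends on s, which is unknown. Over an assumed range of 10% to 70%, following the clause would remove 90 to 30 of about 100 Cohort A participants and inflate the standard error by a factor of 3.2 to 1.2. It is tempting to say that most of Cohort A would be lost; that holds only if s is below 50%, and nothing in the documents shows that it is. Nor do they support saying that steroid dose is irrelevant to skin response: Appendix 7 of the protocol says steroid changes may affect CLASI-A. The sound point is that no rationale is given for the restriction.

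The consequence is limited. CLA-IGA 0/1 is one of many secondary endpoints with nominal p-values, and neither primary analysis is affected. The point is worth correcting because the correction is cheap and removes an open choice of population.

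**What to change.** - **SAP Section 7:** add one sentence stating that the 10 mg restriction in the CLA-IGA 0/1 row of Protocol 9.4.1 does not apply.
- **SAP 14.3.5:** state that only the logistic model of 14.3.3 is reused, in the populations listed in 14.3.5.
- **Objectives table (SAP Section 5):** align it with 14.3.5, so that both name Cohort A and, separately, Cohort B with CLASI-A of at least 8.
- **Protocol:** delete the clause from 9.4.1, and align the objectives tables in Sections 1.1 and 3, at the next amendment made for other reasons.

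The SAP changes should be in place before the database lock for the final analysis, which is where SAP 14.3 puts the secondary endpoints. The cost is a few lines of SAP text. A stand-alone protocol amendment is not needed, because Protocol 9.4 requires one only when a change affects a principal feature, and the population of a nominal secondary analysis is not one.

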9.4.2 Safety Analyses

All safety analyses will be performed on the Safety Analysis population for each cohort separately.

Endpoint	Statistical Analysis Methods	
Primary	Not Applicable	
Secondary		
Adverse Events	Descriptive statistics, AESI summaries, 3-Tier AE summaries	
Clinical Laboratory Test Values	Descriptive statistics, shift tables, boxplots, individual participant line plots, eDISH figures	
ECG Parameters	Descriptive statistics	
Vital Signs	Descriptive statistics	
Tertiary/Exploratory	Not applicable	

AE = Adverse Event, AESI = Adverse Events of Special Interest, ECG = electrocardiogram, eDISH = Evaluation of Drug-Induced Serious Hepatotoxicity

9.4.2.1 Adverse Events

Adverse events will be coded using the MedDRA. All TEAEs will be summarized by intervention group. Treatment-emergent AEs are defined as AEs that occurred or worsened on or after the first dose of study intervention. The number and percentage of participants who experienced at least 1 TEAE will be summarized by System Organ Class and preferred term. The percentage will be based on the number of participants in each intervention group. Treatment-emergent AEs will also be summarized by relationship to intervention and by severity within each intervention group. Deaths, SAEs, AESIs, and AEs leading to study discontinuation will be tabulated and presented in data listings. Participant level data listings of all AEs will be presented.

Summary and analysis of AEs will be performed based on the 3-tier approach (Crowe 2009) as further detailed in the IAP. Tier 1 AEs and AESIs will be predefined in the IAP.

9.4.2.2 Clinical Laboratory Test Values

Clinical laboratory results (chemistry, hematology, and urinalysis) will be summarized using descriptive statistics for each visit by intervention group. Observed values at each visit and changes from Baseline to each post-Baseline visit will be presented. For clinical laboratory parameters with associated normal ranges, number and percentage of participants having high/low/normal findings for worst on-treatment laboratory value will be summarized by intervention group; shift tables will be used to summarize changes from Baseline finding to worst on-treatment finding. For clinical laboratory parameters with NCI-CTCAE grades, shift tables will be used to summarize changes from Baseline grade to worst on-treatment grade. The

distribution of selected laboratory parameters by time point and intervention group will be displayed via boxplots.

All laboratory data will be provided in participant data listings.

Analyses of liver enzyme tests will include Kaplan-Meier estimates of time to ALT or AST events, plots supporting evaluation of Drug-Induced Serious Hepatotoxicity, and individual participant profiles.

